10.4 ECOG PERFORMANCE STATUS

ECOG PERFORMANCE STATUS	
Grade	ECOG
0	Fully active, able to carry on all pre-disease performance without restriction
1	Restricted in physically strenuous activity but ambulatory and able to carry out work of a light or sedentary nature, e.g., light house work, office work
2	Ambulatory and capable of all self-care but unable to carry out any work activities. Up and about more than 50% of waking hours
3	Capable of only limited self-care, confined to bed or chair more than 50% of waking hours
4	Completely disabled. Cannot carry on any self-care. Totally confined to bed or chair.
5	Dead

[R01-0787](#)

11. DESCRIPTION OF GLOBAL AMENDMENT(S)

11.1 GLOBAL AMENDMENT 1

Date of amendment	15 November 2019
EudraCT number	2019-003490-25
EU number	
BI Trial number	1424-0001
BI Investigational Product(s)	BI 905681
Title of protocol	An open-label, Phase I trial to determine the maximum-tolerated dose and investigate safety, pharmacokinetics and efficacy of BI 905681 administered intravenously in patients with advanced solid tumours
To be implemented only after approval of the IRB / IEC / Competent Authorities	
To be implemented immediately in order to eliminate hazard – IRB / IEC / Competent Authority to be notified of change with request for approval	
Can be implemented without IRB / IEC / Competent Authority approval as changes involve logistical or administrative aspects only	
Section to be changed	FLOW CHART: BI 905681 (REFMAL 638) SCHEDULE A TRIAL ASSESSMENTS
Description of change	The Follow-Up blood sample for bone biomarkers was removed. Footnote k stating that Bone biomarkers will be assessed on Cycle 1 Day 1, Cycle 2 Day 1 and then on Day 1 of every odd-numbered cycle and the EOT visit was correct.
Rationale for change	Flow Chart was revised to correct an error in the original version of the CTP.
Section to be changed	FLOW CHART: BI 905681 (REFMAL 638) SCHEDULE B TRIAL ASSESSMENTS
Description of change	The Follow-Up blood sample for bone biomarkers was removed. Footnote k stating that Bone biomarkers will be assessed on Cycle 1 Day 1, Cycle 2 Day 1 and then on Day 1 of every odd-numbered cycle and the EOT visit was correct.
Rationale for change	Flow Chart was revised to correct an error in the original version of the CTP.

Section to be changed	Section 3.1 Overall Trial Design and Plan
Description of change	
After the criterion for MTD is fulfilled, there will be no further dose escalation regardless of the SMC recommendation. The SMC may recommend stopping further dose escalation after the criterion for MTD is fulfilled. Additional patients may be included to confirm this MTD estimate (and to further evaluate PK/PDe), i.e. to confirm that the EWOC criterion is still fulfilled.

Rationale for change	Text was revised to ensure that if the MTD criterion is fulfilled, there is no further dose escalation regardless of the SMC recommendation.
Section to be changed	Table 4.1.1
Description of change	Dilution in 5% glucose 0.9% sodium chloride is required
Rationale for change	Text was revised to correct an error in the original version of the CTP.
Section to be changed	Section 4.1.3 and Section 4.1.4
Description of change	The absolute maximum clinical dose must not exceed 1120 mg/dose.
Rationale for change	Text was revised to ensure that the specifications for host cell DNA and endotoxins stay within the recommended limits for the provisional dose levels for Schedule B.
Section to be changed	Section 4.1.4 Starting Dose for Schedule B
Description of change	
The starting dose in Schedule B will be determined by the SMC, and will not exceed 30% of the MTD from Schedule A. The SMC will also review whether the planned dosing schedule, assessments and sample collection in Schedule B remain appropriate, and may decide not to pursue testing of this schedule.

Rationale for change	Text was revised to include specific details on the provisional starting dose of Schedule B in relation to the Schedule A MTD.
Section to be changed	Section 7.1
Description of change	The BLRM recommended dose for the next dose level is the level with the posterior probability of the DLT rate falling in the target interval [0.16, 0.33] among the doses fulfilling EWOC without skipping any dose level.
Rationale for change	The text was revised to clarify that no dose levels would be skipped.

APPROVAL / SIGNATURE PAGE

[figure not shown]
[figure not shown]
[figure not shown]
[figure not shown]
[figure not shown]
Document Number: c29037963

Technical Version Number: 2.0

Document Name: clinical-trial-protocol-revision-01

Title: An open-label, Phase I trial to determine the maximum-tolerated dose and investigate safety, pharmacokinetics and efficacy of BI 905681 administered intravenously in patients with advanced solid tumours

Signatures (obtained electronically)

Meaning of Signature	Signed by	Date Signed
Approval-Clinical Program		15 Nov 2019 09:28 CET
Author-Clinical Trial Leader		15 Nov 2019 09:47 CET
Author-Clinical Pharmacokineticist		15 Nov 2019 09:55 CET
Approval-Therapeutic Area		15 Nov 2019 14:11 CET
Author-Trial Statistician		15 Nov 2019 17:13 CET
Approval-Clinical Trial Leader		15 Nov 2019 17:15 CET

(Continued) Signatures (obtained electronically)

Meaning of Signature	Signed by	Date Signed

## **2. LIST OF ABBREVIATIONS**

See Medicine Glossary

Term	Definition / description
AE	Adverse Event
BI	Boehringer Ingelheim
BLRM	Bayesian Logistic Regression Model
BOR	Best Overall Response
CR	Complete Response
CRF	Case Report Form
CTC	Common Terminology Criteria
CTh	Concomitant Therapy
CTP	Clinical Trial Protocol
DBL	Databaselock
DCR	Disease Control Rate
DEC	Dose Escalation Committee
DLT	Dose Limiting Toxicity
EOT	End Of Text
EWOC	Escalation With Overdose Control
ICH	International Conference On Harmonisation
IPD	Important Protocol Deviation
MQRM	Medical Quality Review Meeting
MTD	Maximum Tolerated Dose
MTDS	MTD evaluation set
OBD	Optimal Biologic Dose
OR	Objective Response
ORR	Objective Response rate
PD	Protocol Deviation
PK	Pharmacokinetics
PKS	PK set
PR	Partial Response
PT	Preferred Term
REP	Residual Effect Period
RPM	Report Planning Meeting

Term	Definition / description
ScS	Screened Set
SD	Stable Disease
STD	Standard Deviation
SMQ	Standardised MedDRA Query
SOC	System Organ Class
ToC	Table of Contents
TS	Treated Set
TSAP	Trial Statistical Analysis Plan
WHO DD	World Health Organisation Drug Dictionary

### **3. INTRODUCTION**

As per (1), the purpose of this document is to provide a more technical and detailed elaboration of the principal features of the analysis described in the protocol and to include detailed procedures for executing the statistical analysis of the primary and secondary variables and other data.

[figure not shown]
This Trial Statistical Analysis Plan (TSAP) assumes familiarity with the Clinical Trial Protocol (CTP), including Protocol Amendments. In particular, the TSAP is based on the planned analysis specification as written in CTP Section 7 “Statistical Methods and Determination of Sample Size”. Therefore, TSAP readers may consult the CTP for more background information on the study, e.g., on study objectives, study design and population, treatments, definition of measurements and variables, planning of sample size, and randomization.

Version 9.4 or the latest version will be used for analyses.

R Version 4.0.1 and JAGS Version 4.3.0 or the latest versions will be used for the Bayesian Logistic Regression Model (BLRM) analyses.

## **4. CHANGES IN THE PLANNED ANALYSIS OF THE STUDY**

Due to enrollment issues, the trial will be terminated early without determination of the maximum tolerated dose (MTD)/optimal biologic dose (OBD) as per protocol. Only schedule A has been investigated in the trial. The early termination does not have an impact on the planned endpoints.

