7. STATISTICAL METHODS AND DETERMINATION OF SAMPLE SIZE

7.1 STATISTICAL DESIGN - MODEL

The trial will be performed as an open-label study. The objective of the design is to determine the MTD of BI 905681 defined as the highest dose with less than 25% risk of the true DLT rate being $\geq 33\%$ (EWOC criterion). The dose-finding in Schedule A and B will be guided by Bayesian 2-parameter logistic regression models with overdose control ([R13-4803](#)). Separate MTDs will be determined for Schedule A and Schedule B.

The model is given as follows:

$$\text{logit}(\pi_d) = \log(\alpha) + \beta * \log(d/d^*),$$

where $\text{logit}(\pi) = \log(\pi/(1-\pi))$.

π_d represents the probability of having a DLT in the MTD evaluation period at dose d , $d^* = 4.5 \text{ mg/kg/week}$ is the reference dose, allowing for the interpretation of α as the odds of a DLT at dose d^* , and $\theta = (\log(\alpha), \log(\beta))$ with $\alpha, \beta > 0$ is the parameter vector of the model.

The estimated probability of a DLT at each dose level from the model will be summarised using the following intervals:

Under dosing: [0.00, 0.16]

Targeted toxicity: [0.16, 0.33]

Over toxicity: [0.33, 1.00]

The BLRM recommended dose for the next dose level is the level with the posterior probability of the DLT rate falling in the target interval [0.16, 0.33] without skipping any dose level. Applying the EWOC criterion it should be unlikely (<25% posterior probability) that the DLT rate at that dose will exceed 0.33.

The MTD may be considered reached if all the following criteria are fulfilled:

1. Next recommended dose = current dose (stabilisation condition)
2. Number of DLTs in study is at least 1.
3. At least 9 patients have been treated in the trial.

and at least one of the following criteria is fulfilled:

- The posterior probability of the true DLT rate in the target interval [0.16 – 0.33] of the MTD is above 0.5, OR
- At least 6 patients have been treated at the MTD.

The SMC may recommend stopping the trial after the criterion for MTD is fulfilled. Further patients may be included to confirm this MTD estimate. If no DLT is observed while information from the PK profile is considered sufficient, the SMC may recommend a dose for further testing. Any DLTs occurring after the start of the second cycle will be considered for the evaluation of the recommended dose for further testing for BI 905681.

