## **5. ENDPOINT(S)**

### **5.1 PRIMARY ENDPOINT(S)**

The primary endpoints of the trial are:

- The MTD/OBD of BI 905681. The MTD will be assessed based on the number of patients experiencing dose limiting toxicities (DLTs), graded according to Common Terminology Criteria for Adverse Events (CTCAE) Version 5.0, in the first cycle of treatment (first 3 weeks of treatment, MTD evaluation period). The MTD is defined as the highest dose with less than 25% risk of the true DLT rate being equal to or above 33% as determined by the BLRM defined in the CTP.
- Number of patients experiencing adverse events (AEs) during the entire treatment period

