## **6. GENERAL ANALYSIS DEFINITIONS**

### **6.1 TREATMENT(S)**

This is an open label, non-randomized, dose escalation phase I study. The starting dose for Schedule A is BI 905681 1.0 mg/kg every three weeks. The trial has been terminated before the start of schedule B. Dose escalation decisions will be made by a Dose Escalation Committee (DEC) guided by the BLRM with escalation with overdose control (EWOC) criterion. Table 6.1: 1 shows the dose levels that were administered in Schedule A.

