## **7.4 PRIMARY ENDPOINT(S)**

### **7.4.1 Primary analysis of the primary endpoint(s)**

In order to identify the MTD of the trial, the number of patients at each dose level that had DLT during the MTD evaluation period (first three weeks for Schedule A) will be presented, excluding patients who discontinue during the first treatment cycle for reasons other than a DLT.

The BLRM as described in Section 7.1 of the CTP will be analyzed using the number of patients at each dose that had DLTs during the MTD evaluation period among the patients in the MTD set. The prior defined in Table 7.1: 1 of the CTP will be used for the analysis. The resulting posterior distribution of the DLT rates of the doses tested during the trial will be summarized using their mean, SD, 2.5% quantile, median, and 97.5% quantile. Additionally, the posterior probabilities of the DLT rate lying in the intervals [0, 0.16) (underdosing), [0.16, 0.33) (target dosing), and [0.33, 1] (overdosing) will be computed and listed for each dose. The posterior probabilities of underdosing, target dosing, and overdosing of the tested dose levels will additionally be visualized in a bar diagram that further displays which of the dose levels satisfy the EWOC criterion.

In addition, the number of patients with DLTs that occurred during the entire treatment period will be summarized at each dose level.

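### Does the SAP need changing because it says early termination leaves the endpoints unaffected although no MTD was determined?

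*SAP*

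**What the plan says.** SAP section 4 gives the outcome first: "the trial will be terminated early without determination of the maximum tolerated dose (MTD)/optimal biologic dose (OBD) as per protocol", because of enrolment problems, with only Schedule A investigated. The next statement is "The early termination does not have an impact on the planned endpoints". SAP 6.1 adds "The trial has been terminated before the start of schedule B".

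SAP 5.1 keeps the MTD/OBD as the first primary endpoint. It says "The MTD is defined as the highest dose with less than 25% risk of the true DLT rate being equal to or above 33" per cent, and ends that sentence by referring to the BLRM in the protocol. Protocol 2.1.2 and 7.1 give the same definition.

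SAP 7.4.1 opens with "In order to identify the MTD of the trial", as Protocol 7.3.1 does. It then names Protocol 7.1 as the source of the model and Protocol Table 7.1: 1 as the source of the prior, and sets out the output: "The resulting posterior distribution of the DLT rates of the doses tested during the trial will be summarized". It adds the probabilities of under-, target and overdosing, and a bar chart marking the doses that meet the EWOC criterion.

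The stricter conditions are in Protocol 7.1: "The MTD may be considered reached if all the following criteria are fulfilled". They are a next recommended dose equal to the current one, at least 1 DLT, at least 9 patients in the trial, and either a target-interval probability above 0.5 or at least 6 patients at the dose. The SAP does not repeat them. SAP section 3 says "the TSAP is based on the planned analysis specification as written in CTP Section 7" and assumes the reader knows the protocol.

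**The concern.** Section 4 is where a reader looks for departures from plan. It says in consecutive sentences that the first primary endpoint was not obtained and that the endpoints are unaffected. The protocol intended a separate MTD for each schedule; Schedule A ended without one and Schedule B never started.

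SAP 5.1 and 7.4.1 do not carry the outcome forward. Read alone, 5.1 turns the overdose limit into a recipe: take the highest dose below 25% and call it the MTD. That limit is only a ceiling, and sparse or DLT-free data satisfy it easily. The protocol keeps the two ideas apart: section 3.1 lets any dose meeting EWOC be chosen as the recommended dose for expansion whatever the MTD estimate, and section 7.1 provides for a recommended dose, not an MTD, when no DLT is seen. The risk would be a report that names an MTD the protocol's own conditions do not support.

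**Working it through.** **Model and inputs.** Protocol 7.1: logit(π_d) = log α + β·log(d/d*), with d* = 4.5 taken on the q3w dose scale, and a normal mixture prior on (log α, log β) from Table 7.1: 1. The weights are 0.9, 0.05 and 0.05; the means (−2.701, −0.233), (−0.973, −0.115) and (−4.101, −1.113); the SDs (2, 1), (2, 1) and (5, 0.01); the correlations 0. The likelihood is binomial, with posteriors by grid integration. P(OD) is the posterior probability that the DLT rate is at least 0.33. P(TD) is the probability that it lies in [0.16, 0.33).

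**Reproducing the plan's figures.** Prior P(OD), Protocol Table 7.1: 2:

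| Dose (mg/kg) | 1 | 2.5 | 4.5 | 6.5 | 8.5 |
|---|---|---|---|---|---|
| Printed | 0.072 | 0.114 | 0.177 | 0.244 | 0.295 |
| Recomputed | 0.074 | 0.117 | 0.179 | 0.247 | 0.299 |

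Agreement is within 0.005, so the model is the protocol's.

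**The protocol's own example of the gap (Table 10.3:1).** Taking 3 patients per cohort, which fits the 9 patients in three cohorts mentioned in Protocol 10.3:

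- Scenario 5 (0/3, 0/3, 1/6, then 1/3 at 6.5): printed P(OD) 0.212 and P(TD) 0.381 at 6.5; recomputed 0.205 and 0.393. At 8.5, P(OD) is 0.358. So 6.5 is the highest dose under 0.25, but it has 3 patients (not 6) and P(TD) is not above 0.5. No MTD is claimed and three more patients are enrolled.
- Scenario 6 (2/6 at 6.5): printed P(OD) 0.246 and P(TD) 0.471; recomputed 0.241 and 0.480. There are now 6 patients at the dose, and the MTD is claimed.

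**At the SAP doses (1.0, 2.5, 5.0, 7.0, 8.5).** The documents give no patient or DLT counts, so all data here are assumed.

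| Assumed data | Highest dose with P(OD) < 0.25 | P(OD) there | P(TD) there | Protocol 7.1 met? |
|---|---|---|---|---|
| None (prior only) | 5.0 (7.0 gives 0.262) | 0.196 | 0.146 | No: no patients |
| 0/2 at every dose | 8.5 | 0.016 | 0.076 | No: no DLT |
| 0/3 at every dose | 8.5 | 0.006 | 0.046 | No: no DLT |
| 0/3 at lower doses, 1/3 at 8.5 | 8.5 | 0.077 | 0.246 | No: 3 at dose, P(TD) ≤ 0.5 |
| 0/3 at lower doses, 2/3 at 8.5 | 7.0 (8.5 gives 0.336) | 0.143 | 0.419 | No: 3 at dose, P(TD) ≤ 0.5 |

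The overdose limit and the Protocol 7.1 conditions therefore can diverge.

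**Does the divergence reach the report?** Following the SAP as written:

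1. Section 4 fixes the conclusion on the first primary endpoint: not determined.
2. Section 7.4.1 tabulates DLTs, summarises the posterior at the tested doses, lists the three interval probabilities and marks doses meeting EWOC. A dose passing only the overdose limit is shown as EWOC-satisfying, which is what it is.
3. No visible sentence in 7.4.1 selects or declares a dose. An entry after it in the SAP contents is redacted and is not counted either way.
4. Sections 5.1 and 7.4.1 were both cut down to Schedule A: the four-week period and the separate-MTD wording are gone, and so is the Protocol 7.3.1 rerun of the BLRM to re-evaluate the MTD and RP2D.
5. The adverse event and PK endpoints for Schedule A do not use the MTD.

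A reworded section 4 would leave every one of these outputs as it is.

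**The case for a change.** The strongest case for a change is that the status of a primary endpoint should be beyond doubt in the section that records departures from plan. The sentence is accurate only if it refers to endpoint definitions, and it does not say so. The table shows that a reader who took SAP 5.1 alone could name 8.5 mg/kg as an MTD from data with no DLT at all. Clearer wording would be cheap.

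Part of this stands. The sentence is loose, the opening words of 7.4.1 no longer suit a trial that ended without an MTD, and the Protocol 7.1 conditions are not restated.

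The rest does not carry. Naming an MTD would mean overriding the statement immediately before the disputed one. SAP 5.1 repeats the protocol's definition, so any tension between definition and declaration conditions was not created by the SAP. The conditions are easy to find: 5.1 refers to the BLRM in the protocol, 7.4.1 names Protocol 7.1, and section 3 rests on the protocol's statistical section. The doses in the table come from assumed counts and show that two rules differ, not that any reported result would. A met/not-met listing of the conditions would only confirm what section 4 already says.

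**Conclusion.** No change to the plan follows. The endpoint list and definitions are unchanged by early termination; the result for the MTD/OBD is missing, and SAP section 4 says so. The remaining fault is loose wording together with an introductory phrase carried over from Protocol 7.3.1. Analysts following the SAP would produce the same descriptive BLRM, adverse event and PK outputs, and the same conclusion that the MTD/OBD was not determined, whichever way the sentence were phrased. The effect on reported results is nil.

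This rests on two readings. The first is that 7.4.1 has no declaration step, which is true of the visible text. The second is that section 4 governs how the primary endpoint is reported. The calculation confirms that meeting the overdose limit is weaker than reaching an MTD under Protocol 7.1, but the SAP already labels such doses as satisfying EWOC and nothing more.

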## **5. ENDPOINT(S)**

### **5.1 PRIMARY ENDPOINT(S)**

The primary endpoints of the trial are:

- The MTD/OBD of BI 905681. The MTD will be assessed based on the number of patients experiencing dose limiting toxicities (DLTs), graded according to Common Terminology Criteria for Adverse Events (CTCAE) Version 5.0, in the first cycle of treatment (first 3 weeks of treatment, MTD evaluation period). The MTD is defined as the highest dose with less than 25% risk of the true DLT rate being equal to or above 33% as determined by the BLRM defined in the CTP.
- Number of patients experiencing adverse events (AEs) during the entire treatment period

### **5.2 SECONDARY ENDPOINT(S)**

[figure not shown]
#### **5.2.1 Key secondary endpoint(s)**

[figure not shown]
Not applicable.

#### **5.2.2 Secondary endpoint(s)**

The secondary endpoints of the trial are:

- The following Pharmacokinetics (PK) parameters of BI 905681 will be evaluated after the first administration of BI 905681 (if feasible), ie. in Cycle 1:
  - $C_{max}$ : maximum measured concentration of BI 905681 in serum after first infusion
  - $AUC_{0-tz}$ : area under the serum concentration-time curve over the time interval from 0 to the last measured time point ( $t_z$ )

## **6. GENERAL ANALYSIS DEFINITIONS**

### **6.1 TREATMENT(S)**

This is an open label, non-randomized, dose escalation phase I study. The starting dose for Schedule A is BI 905681 1.0 mg/kg every three weeks. The trial has been terminated before the start of schedule B. Dose escalation decisions will be made by a Dose Escalation Committee (DEC) guided by the BLRM with escalation with overdose control (EWOC) criterion. Table 6.1: 1 shows the dose levels that were administered in Schedule A.

**Table 6.1: 1 Dose levels for escalation in Schedule A**

Cohort Dose Level	Proposed dose	Increment from previous dose
1	1.0 mg/kg/q3w	Starting dose
2	2.5 mg/kg/q3w	150%
3	5.0 mg/kg/q3w	100%
4	7.0 mg/kg/q3w	40%
5	8.5 mg/kg/q3w	21.4%

The data will be presented for all dose cohorts separately and in total over all dose cohorts. DLTs occurring during the MTD evaluation period (during the first treatment cycle) will be presented separately.

“Analysing treatment” will be used for reporting of treatment-emergent adverse events (AEs) and to differentiate between screening, on-treatment, and post-treatment safety data. The inequalities start date $\leq$ onset date of the AE $<$  end date of the AE will determine whether the AE will be assigned to the “analysing treatment” or not.

The treatment periods of the trial which will be used for the reporting of AEs and safety laboratory parameters are given in [Table 6.1: 2](#). Safety data recorded during the Residual Effect Period (REP) will be considered as on-treatment. In this trial, the REP is defined as 42 days.

If not specified otherwise, all safety tables will be based on the on-treatment period. AEs that have an onset date during the screening or post-treatment periods will be displayed in separate listings.

**Table 6.1: 2** Definition of treatment periods

Analysing Treatment Period	Start Date (including)	Stop Date (excluding)
Screening	Date of informed consent	The date of first trial medication administration
On-treatment	Date of first administration of trial medication	Date of last trial medication administration + REP*, or death, +1 day whichever comes first, e.g., actual on-treatment period + REP*,
Post-treatment	Last day of on-treatment period +1 day	Date of the last contact date or death, or DBL date, whichever comes first +1 day
MTD evaluation period	Date of first administration of trial medication	Date of first administration of trial medication +21 days

\*Note: A 42-day residual effect period (REP) is defined.

The initial dose of trial medication assigned at the beginning of the first treatment cycle will be used as the label of the analysing treatment.

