### **7.8.1 Adverse Events**

Adverse events will be coded using the Medical Dictionary for Drug Regulatory Activities (MedDRA). Standard BI summary tables and listings will be produced. All adverse events with an onset between start of treatment and end of the residual effect period (REP), a period of 42 days after the last dose of trial medication, will be assigned to the on-treatment period for evaluation.

All treated patients will be included in the safety analysis. In general, safety analyses will be descriptive in nature and will be based on BI standards. No hypothesis testing is planned.

Statistical analysis and reporting of adverse events will concentrate on treatment-emergent adverse events, i.e. all adverse events occurring between start of treatment and end of the residual effect period. Adverse events that start before first drug intake and deteriorate under treatment will also be considered as ‘treatment-emergent.’

The analyses of adverse events (AE) will be descriptive in nature. All analyses of AEs will be based on the number of patients with AEs and not on the number of AEs. Frequency of patients with AEs will be tabulated by treatment dose, highest CTCAE grade, system organ class (SoC) and preferred term after coding according to the current version of MedDRA at the database lock. In addition, AEs will be tabulated by preferred terms only. The SoC will be sorted alphabetically. In tables displaying AEs by preferred terms, this will be sorted by descending frequency of AEs in the “Total” BI 905681 group.

Summary tables and listings of AEs, SAEs, related AEs, related SAEs, AEs of special interest, AEs leading to dose reduction, AEs leading to treatment discontinuation and AEs leading to deaths will be provided.

For the analysis of DLTs with regard to the primary endpoint see [Section 7.4.1](#).

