## **7.8.2 Laboratory data**

The analysis of laboratory data will be descriptively in nature and will follow standard procedures. The analysis of laboratory data will use the same “analyzing treatments” as described for AEs, except for that the baseline laboratory values will be included in the “on treatment” period. Patients having at least one post-baseline laboratory value will be displayed in the descriptive analyses. Patients with missing CTCAE grade at baseline or no baseline value but with post-baseline value will be displayed in the category “Missing CTCAE grade at baseline”.

Descriptive statistics, including change from baseline, frequency of patients with transitions relative to the references range, will be provided for laboratory assessments at scheduled visits. Data collected during potential unscheduled laboratory assessments will be listed. No post-study laboratory values will be considered. CTCAE grade for applicable laboratory parameters will be calculated according to CTCAE v5.0. The following outputs will be presented:

- Baseline, last value and difference from baseline
- Worst CTCAE grade experienced during the on-treatment period
- Transitions of the CTCAE grade from baseline to the worst lab values, from baseline to the last lab values, and from the worst to last values during the on-treatment period
- Possible clinically significant laboratory values
- Transitions for laboratory values without CTCAE grade based on reference ranges

Note: For calculating the change in CTCAE grade from baseline, patients with a CTCAE grade of -9 (no CTCAE grade defined) or CTCAE grade of -5 (overlapping reference ranges) will be treated as a CTCAE grade 0 for all analyses. In laboratory listings, the CTCAE grade is displayed as -9 and -5, respectively.

For Uric Acid, Hypokalemia, amylase, bicarbonate, eosinophils, glucose (high direction), INR of prothrombin time, lipase, methemoglobin, sodium (low direction) the CTCAE grade cannot always be assigned by the laboratory parameter itself as two different CTCAE grades have the same laboratory constellation, but are distinguished by additional clinical parameter. In this case a CTCAE grade of -1 will be assigned. These will not be considered for laboratory analyses. In laboratory listings, the CTCAE grade is displayed as -1, respectively.

Patients with hepatic enzyme elevation will be tabulated.

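### The AE-assignment inequality in SAP 6.1 uses the AE's own end date as its upper limit where the period stop date is meant: a probable drafting slip, wrong as written, minor

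*SAP*

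**What the plan says.** SAP 6.1 introduces the analysing treatment as the device for reporting treatment-emergent AEs and for separating screening, on-treatment and post-treatment safety data. It then gives an inequality that runs from a start date, through the AE onset date, to an upper limit, and closes with "end date of the AE will determine whether the AE will be assigned to the" analysing treatment or not.

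The surrounding text describes a different upper limit:

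- **SAP 6.1, next paragraph:** the sentence that opens "The treatment periods of the trial which will be used for the reporting of AEs and safety laboratory parameters are given in" points to Table 6.1: 2. That table gives each period an inclusive start date and a column whose heading begins "Stop Date (excluding". For the on-treatment period the limit is last dose plus the 42-day REP, or death, plus one day.
- **SAP 6.1, listing sentence:** "AEs that have an onset date during the screening or post-treatment periods will be displayed in separate listings".
- **SAP 7.8.1:** the on-treatment period takes AEs by onset: "All adverse events with an onset between start of treatment and end of the residual effect period (REP), a period of 42 days", counted from the final infusion. Protocol 7.3.4 states the same rule.
- **SAP 7.8.1, pre-existing events:** "Adverse events that start before first drug intake and deteriorate under treatment will also be considered as" treatment-emergent.
- **SAP 7.8.2:** laboratory data use the same analysing treatments "as described for AEs, except for that the baseline laboratory values will be included in the" on-treatment period.

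None of these other statements uses the end date of the AE.

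**The concern.** The sentence is worded as an operative rule: it decides whether an AE is assigned. Treatment-emergent AE reporting feeds the second primary endpoint in SAP 5.1, the number of patients with AEs.

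Taken literally, it has two faults.

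1. An AE with the same onset and end date can never satisfy onset < end. That type of event is foreseeable here. Protocol 4.1.6.3 requires observation for at least 6 hours after infusion for signs of cytokine release. Protocol 5.2.6.1 makes infusion-related reactions within 72 hours AEs of special interest (AESIs) whatever their grade. SAP 7.8.1 plans AESI tables.
2. No period has an upper bound, so an AE with onset after the REP still meets the on-treatment inequality if it lasts beyond its onset date. The rule then fails at its stated purpose of separating on-treatment from post-treatment data.

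**Working it through.** There is no planned figure to reproduce. The check is to apply both rules to example events.

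**Inputs.** The REP is 42 days (SAP 6.1) and infusions are every three weeks (Schedule A). Assumed patient, used only to place dates: first dose on day 0, third and last dose on day 42, no death.

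**Period limit from Table 6.1: 2.** Exclusive stop = last dose + REP + 1 = 42 + 42 + 1 = day 85. On-treatment therefore means onset on days 0 to 84.

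**Rules compared for the on-treatment period.**

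- Literal: 0 ≤ onset < AE end date
- Table: 0 ≤ onset < 85

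| Event (onset, end) | Literal | Table |
|---|---|---|
| Infusion reaction, resolves same day (0, 0) | no, since 0 < 0 is false | yes |
| One-day AE (10, 10) | no, since 10 < 10 is false | yes |
| Multi-day AE within the REP (60, 65) | yes | yes |
| Onset on last REP day (84, 90) | yes | yes |
| Onset 45 days after last dose (87, 89) | yes, since 87 < 89 | no, since 87 ≥ 85 |
| Screening onset (-5, 3) | no | no |

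These rows show which kinds of event are affected. They were chosen for that purpose and say nothing about frequency.

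**How far the second fault can reach.** The first excluded onset is day 43 after the last dose. Protocol 6.2.3.2 places the follow-up visit at 42 to 49 days and makes it the patient's completion of the study. Under Protocol 5.2.6.2, events reported after that go on the SAE form and not on the eCRF. If visits follow the protocol, a wrongly included AE can therefore only have onset about 43 to 49 days after the last dose.

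**What the counting unit does.** SAP 7.8.1 says "All analyses of AEs will be based on the number of patients with AEs and not on the number of AEs". A patient leaves the overall count only if none of that patient's AEs is counted as treatment-emergent. One is wrongly added only if a late multi-day AE is the sole reason for being counted. A single preferred-term or AESI row has less protection, because a patient may have only one event there.

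**MTD analysis.** SAP 7.4.1 fixes the dose-limiting toxicity (DLT) window as the first three weeks, and Protocol 4.1.7 bases dose-escalation decisions on DLTs starting in the first cycle. Neither depends on the inequality.

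**The case against.** The strongest reply is that the documents already resolve the matter. The start date in the inequality is unqualified and has to be taken from Table 6.1: 2, where the stop date stands beside it. The ≤ and < signs match the inclusive and exclusive columns of that table. SAP 7.8.1, the operative AE section, states the onset rule in full. Laboratory values have no AE end date, so only a period stop date can serve under SAP 7.8.2. A programmer would probably follow the table. Safety analyses are also descriptive, with no hypothesis testing.

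All of that stands, and it is why the point is minor. It does not remove the error: the sentence says that it determines assignment, and it contradicts four other statements in a final SAP.

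Two stronger readings are tempting. A reader might infer that the on-treatment period becomes open-ended in practice; the end of eCRF collection at the follow-up visit limits this to roughly one week. A reader might also infer that AEs still ongoing, with no end date, would be lost. The inequality alone cannot be evaluated for them, but SAP 6.6 refers missing and incomplete AE dates to a sponsor guideline outside these documents, so that loss cannot be asserted.

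**Conclusion.** Wrong as written; minor. The upper limit in the SAP 6.1 inequality should be the period stop date. The intended rule can be recovered from Table 6.1: 2 and SAP 7.8.1, so a drafting slip is the likely explanation.

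Harm arises only if the sentence is programmed literally. Its size cannot be calculated, because the documents do not give the share of same-day AEs or the number of AEs per patient. The direction of the argument is clear: probably a small effect on the number of patients with AEs, a larger one on individual preferred-term or AESI rows, and low risk for the MTD analysis.

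A reader might infer that the primary endpoints are compromised. The documents do not support that: AE analyses count patients, and the DLT window is set elsewhere. The bound of 43 to 49 days assumes that follow-up visits are held on schedule.

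**What to change.** In SAP 6.1, replace the inequality with: `period start date ≤ AE onset date < period stop date (Table 6.1: 2)`. This agrees with the table, the listing sentence, SAP 7.8.1 and Protocol 7.3.4.

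Optionally, add a cross-reference to SAP 7.8.1 for AEs that begin before the first dose and worsen on treatment. An onset-only rule places them in screening, while 7.8.1 already adds them to the treatment-emergent set, so the reference helps the reader without changing the analysis.

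The cost is one corrected sentence. No new data are needed and the planned tables do not change. If AE programs already exist, confirm that they take the upper limit from Table 6.1: 2.
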